8.3 Statistical Power of Proposed Clinical Investigation to Demonstrate Device Safety

If, during the course of CI02, 30 participants use a total of 13 each VR101 devices (390 VR101 devices, total) during the long-term safety portion of the study, and an additional 30 participants use a total of 4 VR101 devices during the 4-week crossover efficacy portion (120 VR101 devices, total), then, at the conclusion of CI02, a total of 553 VR101 devices will have been used (510 total uses of VR101 devices in CI02, plus an additional 43 total VR101 devices already used in CI01 [with no SADEs observed in CI01]). Note that this total number of devices used does not account for VR101 devices used for less than 5 days whose data will not be used in assessing efficacy, but whose data will be included in the sample of devices used to assess safety. So, it is likely that the number of VR101 device uses evaluated for safety will exceed 553.

J3 Bioscience, Inc.	Clinical Investigation Plan and Protocol CI02	CI02-CIP Rev. 08 Page 54 of 75
	A Pivotal Clinical Investigation to Evaluate the Safety and Efficacy of J3 Bioscience Lubricating Intravaginal Ring VR101 in Relieving Symptoms of Vaginal Dryness	

If 2 SADEs occur out of a total 510 VR101 devices used according to instructions in the proposed investigation, then we will be able to rule out SADE rates greater than 1 event per 100 devices with 95% confidence. The 95% confidence interval for 2 events in 510 devices is (0.00, 0.01) (exact test, Minitab 17).

However, if no SADE is observed during the entirety of CI02 (0 events/510 devices), as expected, we will be able to rule out a SADE rate greater than 0.6 events per 100 devices with 95% confidence. The 95% confidence interval for 0 events in 510 observations is (0.000, 0.006) (exact test, Minitab 17).

Further, if no SADE is observed during the entirety of CI02 and CI01 (0 events/553 devices), as expected, we will be able to rule out a SADE rate greater than 0.5 events per 100 devices. The 95% confidence interval for 0 events in 553 observations is 0.000 (0.000, 0.005) (Minitab 17).

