Participants in Group S1V2 will be assigned to complete the long-term safety evaluation. Following the 4-week use of shams and a 3-week washout period, these participants will use a new VR101 device every 7 days for 13 consecutive weeks. V1S2 participants will be transitioned back to VR101 following 4 weeks of sham use, and will use VR101 for 13 additional weeks.

NOTE: VHI scores will be collected during the long-term safety evaluation, but those scores assigned after day 28 will not be used as a measure of device efficacy.

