5.2 Investigational and Predicate Devices

5.2.1 Exposure to VR101 and the sham control

Participants will use VR101 for up to 17 weeks total and the sham control for 4 weeks as described above. Participants will use VR101 for approximately 13 total weeks, consecutively, to evaluate device safety.

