8.4 Expected Drop-Out Rates

NOTE: The first paragraph below contains out-of-date information, as of this Revision, but is included for reference.

During the pilot investigation (CI01), one participant missed multiple study visits and discontinued the VR101 treatment regimen. However, the participant eventually restarted and successfully completed the investigation, meaning that the drop-out rate for CI01 was 0%. Statistically, if the dropout rate is “0” for a sample size of 21, we can then rule out any drop-out rates higher than 14.6% with 95% confidence (upper bound of the exact Blyth-Still-Casella confidence interval for the proportion 0/21). However, since CI02 requires longer continued participant involvement than CI01, it is possible that the drop-out rate for enrolled participants in CI02 may even exceed 14.6%. We have assumed a 14.6% dropout rate to estimate the number of participants to enroll in the proposed investigation.

The 95% confidence interval used above still underestimated the drop-out rate due to the differing enrollment durations of CI01 and CI02. During the crossover study, which lasted for 11 weeks (per participant), 11 of 72 participants withdrew from the study (1.39% of initial enrollment per week [average], 0.70-2.47% per week [95% CI]. Assuming that half of the participants will participate in the long-term safety study for 9 weeks (Group S1V2) and the remaining half will participate for 13 weeks (Group V1S2), continuation of at least 42 total participants will ensure, with 95% confidence, that 30 participants will complete the long-term safety evaluation (13 consecutive weeks of VR101 use).

Since participants will need to be re-consented when this protocol revision takes effect, the number of additional dropouts (not accounted for by the calculation above) when participants are presented with the new Informed Consent Form is unknown. Therefore, we will offer

J3 Bioscience, Inc.	Clinical Investigation Plan and Protocol CI02	CI02-CIP Rev. 08 Page 55 of 75
	A Pivotal Clinical Investigation to Evaluate the Safety and Efficacy of J3 Bioscience Lubricating Intravaginal Ring VR101 in Relieving Symptoms of Vaginal Dryness	

participation in the long-term safety study to all available participants (up to 61) to ensure that the goal, of 30 participants using VR101 continuously for 13 weeks in the safety portion of the investigation, is met.

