8.12 Definition of Study Populations for Analysis

THE FOLLOWING STUDY POPULATIONS HAVE BEEN DEFINED FOR THIS INVESTIGATION:

Intent-to-Treat (ITT) Primary Efficacy Hypothesis Population: All patients who meet inclusion/exclusion criteria and are randomized will be included. Any missing day 0 or day 28 VHI scores will be imputed as defined in section 8.8.

J3 Bioscience, Inc.	Clinical Investigation Plan and Protocol CI02	CI02-CIP Rev. 08 Page 57 of 75
	A Pivotal Clinical Investigation to Evaluate the Safety and Efficacy of J3 Bioscience Lubricating Intravaginal Ring VR101 in Relieving Symptoms of Vaginal Dryness	

Menopausal Population: All members of the ITT population who self-report to being menopausal (have not experienced a menstrual period in the 12-month period prior to the study).

Safety Population: All VR101 devices in all study arms that are successfully inserted and used in accordance with the provided instructions for use will be included as a basis for determination of SADE proportion.

Claim 1 Population: All participants who report a daily vaginal dryness severity following their first VR101 use (Visit 2/5, depending on study arm) and report a weekly average vaginal dryness severity prior to their first VR101 insertion (Visit 1/4, depending on study arm), will be included in the analysis for Claim 1. See section 5.4.5 for relevant survey questions.

Claim 2 Population: All participants in group V1S2 who respond to the appropriate survey question (see section 5.4.6) immediately following their first VR101 insertion (Visit 1) will be included in the analysis for Claim 2.

Claim 3 Population: All daily diary responses recorded regarding VR101 comfort during use (see section 5.4.6) will be included in the analysis for Claim 3.

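### Section 8.3 was not updated for Rev. 08: its 510 VR101 uses omit every long-term ring in group V1S2, and its tolerance of 2 SADEs at 510 fails the plan's own safety rule

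*Combined protocol and SAP*

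**What the plan says.** **Section 8.3** multiplies 30 women by 13 rings (390), supposes that "an additional 30 participants use a total of 4 VR101 devices during the 4-week crossover efficacy portion" (30 × 4 = 120), then adds the pilot: "510 total uses of VR101 devices in CI02, plus an additional 43 total VR101 devices already used in CI01", for 553. The only uses it names as left out of the total are rings worn for less than 5 days. It then says that 2 SADEs in 510 uses would exclude a rate above 1 per 100, printing the interval as (0.00, 0.01).

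**The Rev. 08 schedule** differs.
- Section 5.1: "V1S2 participants will be transitioned back to VR101 following 4 weeks of sham use, and will use VR101 for 13 additional weeks".
- Section 5.2.1: "Participants will use VR101 for up to 17 weeks total".
- Sections 1.4 and 5.3.4 agree. Section 5.3.6 selects all participants automatically for the long-term portion.
- Section 8.4 assumes 13 long-term weeks for V1S2 and offers that phase to up to 61 women.

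**The denominator** in section 8.12 is "All VR101 devices in all study arms that are successfully inserted and used in accordance with the provided instructions for use".

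**The pass rule** in section 4.2.2 requires the upper limit of the two-sided exact 95% interval for the SADE proportion to be 0.01 or less.

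**Two further statements bear on the count.** Sections 5.3.5 and 5.4.3 (Final Visit) have V1S2 women asked to stop VR101 once the blind is broken. Section 5.3.5 leaves partial ring uses out of the total, whereas 8.3 includes rings worn under 5 days in the safety sample.

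**The concern.** Section 8.3 is the plan's only statement of what the safety endpoint can show, and that endpoint is one of the two on which section 8.5 makes trial success depend. Its exposure model ends VR101 use at 4 rings for half the women, while the current schedule takes them up to 17. Section 8.4 was revised for Rev. 08 and labels its old paragraph out of date. Section 8.3 was not revised and carries no such label.

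Under an exact upper-limit rule, the number of uses determines how many SADEs can occur before the endpoint fails. A reader of 8.3 gets an exposure that is not the one planned, and a tolerance that the rule does not grant at that exposure.

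**Working it through.** **1. Reproduce the plan's totals.** 30 × 13 + 30 × 4 = 390 + 120 = 510, and 510 + 43 = 553. Both reproduce.

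**2. Apply the 4.2.2 rule at 510.** The exact (Clopper-Pearson) upper limit for x events in n uses is the 0.975 quantile of Beta(x + 1, n − x).

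| SADEs / uses | Two-sided 95% upper limit | 0.01 or less? |
|---|---|---|
| 0 / 510 | 0.0072 | yes |
| 1 / 510 | 0.0109 | no |
| 2 / 510 | 0.0141 | no |

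The printed 0.01 for 2/510 is 0.0141 rounded to two decimals. A one-sided 95% limit does not rescue it (0.0123). The printed limits for 0/510 (0.006) and 0/553 (0.005) match the one-sided values, 0.0059 and 0.0054. The two-sided values are 0.0072 and 0.0066.

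**3. Acceptance numbers.** The smallest n at which the two-sided limit is 0.01 or less is 368 for 0 SADEs, 555 for 1, 720 for 2 and 874 for 3.

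**4. Exposure with 30 long-term completers.** Let v of the 30 be V1S2, and let the other 30 women use only their 4 crossover rings. Uses = 13(30 − v) + 17v + 120 = 510 + 4v.
- v = 0: 510, so 0 SADEs pass.
- v = 15: 570, so 1 passes (limit 0.0097).
- v = 30: 630, so 1 passes (limit 0.0088; 2/630 gives 0.0114).

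**5. Exposure if V1S2 women complete 13 weeks.** Section 8.4 gives weekly dropout w = 11/72/11 = 1.39%. Expected rings over k long-term weeks are L(k) = Σ(1 − w)^i for i = 1 to k, so L(9) = 8.40 and L(13) = 11.80. All 61 women are credited with 4 crossover rings, and those continuing are split equally.
- 42 continue: 61 × 4 + 21 × (8.40 + 11.80) = 668, so 1 SADE passes (limit 0.0083).
- 61 continue: 61 × 4 + 30.5 × (8.40 + 11.80) = 860, so 2 pass (limit 0.0084; 3/860 gives 0.0102).
- Full adherence by 60 women: 30 × 13 + 30 × 17 = 900, so 3 pass (limit 0.0097).

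Section 8.4 expresses dropout as a share of initial enrollment. Taken linearly, the totals become 666 and 857. Across its interval of 0.70–2.47% per week, 61 continuing gives about 886 to 813 uses, tolerating 3 at the top and 2 at the bottom.

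**6. Exposure if V1S2 women stop at unblinding.** Assume uniform enrollment over the 10 to 23 weeks of section 5.3.7, unblinding at the last participant's Visit 6, completed weeks only, and the same dropout. Mean V1S2 long-term rings fall from 11.80 to 4.28 (10 weeks) or 8.31 (23 weeks).
- 42 continue: 244 + 21 × (8.40 + 4.28) = 510, up to 244 + 21 × (8.40 + 8.31) = 595. This tolerates 0 or 1.
- 61 continue: 244 + 30.5 × 12.68 = 631, up to 244 + 30.5 × 16.71 = 754. This tolerates 1 or 2.

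**7. Effect on the chance of passing.** The documents give no true SADE rate, so the rates here are assumed and rings are treated as independent. The binomial probability of no more than the acceptance number is as follows.

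| Uses (SADEs allowed) | True rate 0.1% | True rate 0.2% |
|---|---|---|
| 510 (0) | 60% | 36% |
| 570 (1) | 89% | 68% |
| 860 (2) | 94% | 75% |
| 900 (3) | 99% | 89% |

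**The case against.** Section 8.3 is phrased conditionally, uses the committed minima of 30 long-term and 60 crossover completers, and says the count will probably exceed its total. Understating exposure is conservative. The pass rule sits in 4.2.2, applies to observed uses and needs no forecast, and section 8.5 refers to 4.2.2 rather than 8.3. The instruction to stop at unblinding may also remove many V1S2 rings.

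Most of this stands, and it limits the point. It does not restore 8.3. Short-worn rings are the only excess that 8.3 names, and any V1S2 long-term ring used before unblinding still counts under 8.12. The conservative direction also does not extend to the SADE tolerance, which 8.3 overstates at 510.

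A reader might infer three stronger things that the documents do not support.
- *That the amendment shifted the acceptance number.* Rev. 07 is not supplied, so V1S2 exposure under it cannot be compared.
- *That a later restatement would look fitted to the events.* Section 4.2.2 already fixes the interval, its level and the 0.01 limit. An outdated planning example gives no discretion over these.
- *That 668 and 860 are the settled exposures.* They hold only if V1S2 women complete 13 weeks, and the plan contradicts itself on that.

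**Conclusion.** The point holds as a failure to update section 8.3, together with an error in its stated tolerance. The figure of 510 is a conditional floor for the minimum-completer scenario and does not describe the exposure that Rev. 08 schedules. Depending on how many women continue, how they split between sequences and whether V1S2 women stop at unblinding, the documents support roughly 510 to 900 uses. The rule then tolerates between 0 and 3 SADEs. At 510 it tolerates 0, not 2.

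The acceptance numbers follow directly from 4.2.2 and need no further assumption. The exposure totals rest on the 8.4 dropout rate and an equal split, and the stop-at-unblinding figures also rest on assumed uniform enrollment. Nothing here suggests too little exposure or a flaw in the pass rule itself. What needs correcting is the stated exposure and the stated SADE tolerance.

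**What to change.** 1. Reconcile the 13-week V1S2 schedule (1.4, 5.1, 5.3.4, 8.4) with the instruction to stop VR101 when the blind is broken (5.3.5 and 5.4.3). Reconcile also whether partial uses enter the denominator (5.3.5 against 8.3). This review does not choose either rule.
2. In 8.3, replace the single total with a range: a floor of 510; 570–630 for 30 completers when half to all of them are V1S2; up to about 668 (42 continuing) or 860 (61 continuing) if V1S2 women complete 13 weeks, with 900 for 60 women at full adherence; and the lower totals if they stop at unblinding, illustratively 510–595 and 631–754, with the enrollment assumption stated.
3. Replace the 2-in-510 statement with the acceptance numbers implied by 4.2.2: 0 SADEs for 368–554 uses, 1 from 555, 2 from 720, 3 from 874. Print upper limits to at least three decimals and on the two-sided basis.

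Restating 8.3 costs only arithmetic and wording. The 4.2.2 rule, the 1% limit and enrollment stay as they are. The reconciliation in step 1 is a decision for the sponsor and should come before any new total is fixed.

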4.2.2 Safety Hypothesis

Primary Safety Hypothesis: VR101, when used in accordance with provided instructions for use will not result in a rate of occurrence of Serious Adverse Device Effects (SADE) greater than 1%.

P(safety) = proportion of initiated VR101 uses without a Serious Adverse Device Effect, which is equal to: Total number of initiated VR101 uses without a participant reporting a serious adverse device effect during VR101 use divided by the total number VR101 devices used.

VR101 safety will be demonstrated if the upper bound of the two-sided exact 95% confidence interval surrounding the proportion of SADE occurrence ('P(SADE)') is 0.01 or less.

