5.1.1 Study Endpoints

Used to Test Primary Efficacy Hypothesis:

1. $\Delta VHI_{VR101}(\text{day 28}) - \Delta VHI_{\text{sham}}(\text{day 28})$, the paired difference in vaginal dryness relief between VR101 and the sham control at day 28.

J3 Bioscience, Inc.	Clinical Investigation Plan and Protocol CI02	CI02-CIP Rev. 08 Page 27 of 75
	A Pivotal Clinical Investigation to Evaluate the Safety and Efficacy of J3 Bioscience Lubricating Intravaginal Ring VR101 in Relieving Symptoms of Vaginal Dryness	

Used for Validation of Claim 1:

2. The paired difference between self-reported 24-hour vaginal dryness severity reported after the first 7 days of VR101 use (see Section 5.4.5, collected at Visit 2 or 5 depending on study group) and weekly-averaged vaginal dryness severity prior to ring use (also see Section 5.4.5, collected at Visit 1 or Visit 4 depending on study group).

Used for Validation of Claim 2:

3. Participant reported ease of use of VR101 (measured on a scale of -4 to 4, see Section 5.4.6).

Used for Validation of Claim 3:

4. Self-reported perception that VR101 was comfortable during use, measured on a scale of -4 to 4 (see Section 5.4.6).

Used to Test Primary Safety Hypothesis:

5. The proportion of Serious Adverse Device Effects (SADE) in relation to the total number of VR101 devices use in the study.

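### Section 8.3 counts 43 event-free pilot ring uses among those evaluated for safety, in conflict with the CI02-only endpoint definitions, and the pass/fail rule in 4.2.2 names no study

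*Combined protocol and SAP*

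**What the plan says.** Section 8.3 plans 30 women using 13 rings each and 30 using 4 each, which makes 510 VR101 uses in CI02. It reaches 553 with the words "plus an additional 43 total VR101 devices already used in CI01", remarking that CI01 had no SADEs. It then says that rings worn for less than 5 days come on top of this and concludes: "So, it is likely that the number of VR101 device uses evaluated for safety will exceed 553". Exact intervals follow for 2/510, for 0/510 and, last, for 0/553 with both studies combined.

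The sections that define the endpoint are narrower. The synopsis (1.3.1) speaks of SADEs over the course of the study. Endpoint 5 in 5.1.1 is "The proportion of Serious Adverse Device Effects (SADE) in relation to the total number of VR101 devices use in the study". The Safety Population in 8.12 begins "All VR101 devices in all study arms that are successfully inserted".

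The decision rule is in 4.2.2: "VR101 safety will be demonstrated if the upper bound of the two-sided exact 95% confidence interval" for the SADE proportion is 0.01 or less. The denominator given there is "divided by the total number VR101 devices used", with no study named. Section 8.5 makes this test one of the two on which the success of the investigation depends.

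**The concern.** The denominator of a co-primary safety test should have one reading. Here an analyst could cite 5.1.1 and 8.12 for CI02 uses alone, or 8.3 for CI02 plus CI01, and 4.2.2 does not settle it.

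The two readings are not neutral. CI01 was completed in May 2014 (6.2) and its result is quoted in 8.3, so the 43 uses enter as known non-events. They can lower the upper confidence limit and can never raise it. An exact 95% limit keeps its error rate when every counted use had a chance to produce an event. Adding uses whose outcome is already known weakens that protection. If a SADE occurred and the count fell near a threshold, the choice of denominator would decide the result and would then look driven by the data.

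**Working it through.** **Inputs.** Margin 0.01 and two-sided exact 95% limit (4.2.2); 30 × 13 = 390 and 30 × 4 = 120 CI02 uses, plus 43 CI01 uses with no SADEs (8.3); up to 61 women offered long-term use (8.4).

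**The plan's figures.** 390 + 120 = 510, and 510 + 43 = 553, so the counts reproduce. The zero-event upper limits in 8.3 (0.006 and 0.005) reproduce only as one-sided 95% limits: 0.00586 for 0/510 and 0.00540 for 0/553. The stated interval for 2/510, (0.00, 0.01), is (0.0005, 0.0141) before rounding, so two SADEs in 510 uses would fail the rule. That is a separate error in 8.3.

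**Formula.** For x SADEs in n uses, the Clopper-Pearson upper limit is the 0.975 quantile of Beta(x + 1, n − x). It is at or below 0.01 exactly when P(X ≤ x) ≤ 0.025 for X ~ Binomial(n, 0.01).

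**At the plan's own counts:**

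| SADEs | 510 (CI02 only) | 553 (pooled) |
|---|---|---|
| 0 | 0.0072, pass | 0.0066, pass |
| 1 | 0.0109, fail | 0.01003, fail |
| 2 | 0.0141, fail | 0.0130, fail |

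No verdict changes. For one SADE the pooled limit misses by a hair, and another exact method (Blaker) gives 0.00999 for 1/553, a pass.

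**Smallest n that passes, and the range of CI02 counts in which 43 added non-events change the verdict:**

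| SADEs | Smallest passing n | Fail alone, pass pooled |
|---|---|---|
| 0 | 368 | 325 to 367 |
| 1 | 555 | 512 to 554 |
| 2 | 720 | 677 to 719 |
| 3 | 874 | 831 to 873 |

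Each range runs from the threshold minus 43 to the threshold minus 1. Example: 1/530 has limit 1.047% and fails; 1/(530 + 43) = 1/573 has limit 0.968% and passes. The zero-SADE range lies below the planned 510 uses.

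**Error rate.** Take a true CI02 rate of 1% and 512 CI02 uses. Unpooled, only zero SADEs passes: 0.99^512 = 0.0058, or 0.6%. Pooled, 512 + 43 = 555 and one SADE also passes: 0.0058 + 512 × 0.01 × 0.99^511 = 0.0058 + 0.0301 = 0.0359, or 3.6%. The rule intends at most 2.5%. At 700 uses the chance rises from 0.7% to 2.9%.

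**Which counts could arise.** The documents give no updated total for Rev. 08, so these are assumptions. Each takes the 61 women left after the crossover with four VR101 rings each (61 × 4 = 244), about half of the continuing women adding 9 rings and the rest 13, and ignores rings of women who dropped out.

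- 30 continue: 244 + 15 × 9 + 15 × 13 = 574. Outside every range; one SADE passes without pooling.
- 42 continue (the number in 8.4): 244 + 21 × 9 + 21 × 13 = 706. Inside the two-SADE range.
- All 61 continue: 244 + 30 × 9 + 31 × 13 = 917. Above the three-SADE range.

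**The case against.** The strongest reply is that the plan never says the pass/fail test pools CI01. Section 8.5 refers success to 4.2.2, not to 8.3. Section 4.2 is introduced as concerning CI02, and 1.3.1, 5.1.1 and 8.12 all point to this study. Section 8.3 is a power section. It gives the CI02-only intervals first, ties its 1% margin scenario to 510 uses, and brings in 0/553 only as a further figure. All of that stands. A reader might infer that the sponsor has decided to dilute the primary test with pilot data. The documents do not support that: they show one sentence at odds with the definitions, and a rule that leaves the matter unstated.

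It is also fair that the ranges are narrow, that each needs a particular SADE count when the plan expects none, and that the one-SADE range may be overtaken if many women continue. The three-SADE range would need near-complete re-consent and retention as well as three SADEs.

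A reader might add that CI01, at two rings per woman, says nothing about longer use. That argument carries little weight here, because the endpoint is per device use and CI01 rings were also worn for 7 days each. The objection to pooling rests on the known outcome.

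The reply does not remove the ambiguity. No section excludes CI01, and 8.3 attaches the phrase about evaluation for safety to the total that contains it.

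**Conclusion.** The safety denominator is stated inconsistently. Section 8.3 gives more than 553 uses including 43 known event-free pilot uses, the endpoint and population definitions imply CI02 alone, and the rule in 4.2.2 does not name the study.

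At exactly 510 versus 553 uses nothing changes, and with no SADEs pooling is irrelevant from 368 CI02 uses upward. The inconsistency matters if SADEs occur and the CI02 count falls in one of the ranges above, the first of which begins two uses beyond the plan. There, following 8.3 would turn a fail into a pass and raise the chance of passing at a true 1% rate above 2.5% (3.6% at 512 uses). This rests on Clopper-Pearson limits and on assumed CI02 counts. It is worth correcting because the test is co-primary and the correction is small.

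**What to change.** - In 4.2.2 and 8.12, state that the pass/fail SADE proportion uses VR101 uses in CI02 only.
- In 8.3, replace 553 as the number evaluated for safety with the CI02 count (510 as planned), and label the combined CI01 and CI02 interval as descriptive.
- Reconcile the reason 8.3 gives for a higher count, that rings worn for less than 5 days are included, with 5.3.5, which leaves partial ring uses out of the total for Endpoint 5. The denominator is not fixed until these agree.

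The cost is a few words, and a supporting figure that is slightly less favourable: with no SADEs, the two-sided upper limit is 0.72% on 510 uses instead of 0.66% on 553. The change should be made before the safety data are analysed, so that it cannot appear to depend on the result.

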NOTE: Participants who discontinue ring use mid-week and restart for any reason (including a menstrual period) will naturally deviate from the visit scheduling windows (e.g. 28±2 days) listed in Section 5.4.3. These events should be accurately recorded and documented, but do not need to be treated as formal Deviations from the Plan per Section 11. In Daily Diaries, participants will be asked to document the date and time of any such ring removal/discontinuation of use and the date and time the new ring was inserted.

All safety data will be used to test the primary safety hypothesis, except that partial ring uses will not be counted in the total number of rings used (see Endpoint 5). All participants will be automatically selected to participate in the safety portion of the investigation.

Participants who become pregnant during the study will be instructed to discontinue use of VR101 and will be dropped from the study. Study staff will refer any such participants to a clinical facility for follow-up. Efficacy datasets from these participants will be handled as described for incomplete efficacy study datasets in section 8.8 and 8.9.

J3 Bioscience, Inc.	Clinical Investigation Plan and Protocol CI02	CI02-CIP Rev. 08 Page 32 of 75
	A Pivotal Clinical Investigation to Evaluate the Safety and Efficacy of J3 Bioscience Lubricating Intravaginal Ring VR101 in Relieving Symptoms of Vaginal Dryness	

When the last participant completes the crossover study and the blind is broken, participants in Group V1S2 will be contacted by study staff and asked to discontinue VR101 use and return any remaining study products (shams or VR101 devices) to the clinic at their earliest convenience.

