8.5 Pass/Fail Criteria of the Clinical Investigation

The clinical investigation will be considered a success if the null hypotheses for the primary efficacy and safety endpoints are rejected as defined in Section 4.2.1 and 4.2.2, respectively. If these two null hypotheses are rejected, reasonable safety and efficacy of VR101 following long-term sequential use will be established and substantial equivalence of VR101 with the predicate Replens devices will be demonstrated. Results of additional hypothesis testing described in Section 4.2.3 will have no effect on the success or failure of the clinical investigation.

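### Section 8.3 says 2 SADEs in 510 devices rules out a 1% rate, but the exact two-sided upper bound is 1.41%, so at 510 only 0 SADEs passes; Sections 5.3.5 and 8.3 also conflict on whether partial ring uses count.

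*Combined protocol and SAP*

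**What the plan says.** Section 4.2.2 sets the primary safety criterion: "VR101 safety will be demonstrated if the upper bound of the two-sided exact 95% confidence interval surrounding the proportion of SADE occurrence" is 0.01 or less. Section 8.5 makes this one of two conditions for trial success, which is reached if the "null hypotheses for the primary efficacy and safety endpoints are rejected as defined in Section 4.2.1 and 4.2.2, respectively".

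Section 8.3 illustrates the rule for 510 VR101 devices. If two SADEs occur, it says, "we will be able to rule out SADE rates greater than 1 event per 100 devices with 95% confidence", and gives as support: "The 95% confidence interval for 2 events in 510 devices is (0.00, 0.01) (exact test, Minitab 17"). For no events it prints one more decimal: "The 95% confidence interval for 0 events in 510 observations is (0.000, 0.006) (exact test, Minitab 17"). Pooled with the 43 pilot (CI01) devices, 0/553 is given an upper limit of 0.005.

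The device total is described in four ways:
- Section 5.3.5: "All safety data will be used to test the primary safety hypothesis, except that partial ring uses will not be counted". The sentence ties this exclusion to the ring total behind Endpoint 5.
- Section 8.3: "Note that this total number of devices used does not account for VR101 devices used for less than 5 days", whose data are set aside for efficacy, "but whose data will be included in the sample of devices used to assess safety". It adds that the number evaluated for safety will probably exceed 553.
- Section 4.2.2: counts initiated uses without a SADE, divided by devices used.
- Section 8.12: limits the safety population to devices inserted successfully and used as instructed.

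**The concern.** For 2/510 the interval is printed to two decimals, the same precision as the 0.01 limit it is compared with. The zero-event intervals beside it have three. If the unrounded limit is above 0.01, Section 8.3 tells the reader that a failing result passes.

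This is one of the two endpoints that decide the trial. Section 4.2.2 names neither the exact method nor the precision, so Section 8.3 is the only worked example of how to apply it. An analyst who copied that example would call zero, one or two SADEs in 510 a success.

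The denominator conflict adds to this. A SADE count near the boundary could pass or fail according to which section is followed, and that choice could be made after the events are known.

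**Working it through.** **Inputs.** Limit 0.01, two-sided exact 95% (Section 4.2.2). Device total 30 × 13 + 30 × 4 = 390 + 120 = 510, and 510 + 43 = 553 with CI01 (Section 8.3). Scenario: 2 SADEs (Section 8.3).

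**Formula.** Clopper-Pearson limits for x events in n devices:
- lower = Beta quantile at 0.025 with parameters (x, n − x + 1)
- upper = Beta quantile at 0.975 with parameters (x + 1, n − x)
- for x = 0 the upper limit is 1 − 0.025^(1/n)

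**Step 1: the plan's figure.** For 2/510 the interval is (0.000475, 0.014094). To two decimals this is (0.00, 0.01), as printed. The interval reproduces; the conclusion drawn from it does not, because 0.0141 > 0.01. As a check, at a true rate of exactly 1% the chance of two or fewer SADEs in 510 is 0.115, against the 0.025 that the rule allows.

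**Step 2: other event counts and total.**

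| SADEs | upper, n = 510 | upper, n = 553 | 4.2.2 rule |
|---|---|---|---|
| 0 | 0.0072 | 0.0066 | pass at both |
| 1 | 0.0109 | 0.01003 | fail at both |
| 2 | 0.0141 | 0.0130 | fail at both |

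**Step 3: other readings of the rule.** For 2/510, the Blaker exact interval gives 0.0138, the Sterne exact interval 0.0143, and a one-sided 95% exact bound 0.0123. All fail. For 1/510, Blaker (0.0108) and Sterne (0.0113) fail. A one-sided 95% bound (0.0093) would pass, but Section 4.2.2 says two-sided.

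**Step 4: zero-event limits.** Two-sided: 1 − 0.025^(1/510) = 0.0072 and 1 − 0.025^(1/553) = 0.0066. One-sided: 1 − 0.05^(1/510) = 0.0059 and 1 − 0.05^(1/553) = 0.0054. The printed 0.006 and 0.005 match the one-sided values. Both cases pass either way.

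**Step 5: devices needed for an upper limit of 0.01 or less.**

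| SADEs | Clopper-Pearson | Blaker | Sterne |
|---|---|---|---|
| 0 | 368 | 356 | 377 |
| 1 | 555 | 553 | 576 |
| 2 | 720 | 706 | 730 |
| 3 | 874 | 857 | 881 |

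At the Clopper-Pearson boundaries: 1/554 gives 0.010016 and 1/555 gives 0.009998; 2/719 gives 0.010012 and 2/720 gives 0.009998.

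**Step 6: the denominator.** Section 8.3 says its total leaves out devices used under 5 days, so partial uses come on top of the 510. Take one SADE.
- 510 full uses, partial uses excluded (5.3.5): 0.0109, fail.
- 510 full plus 45 partial uses = 555, partial uses included (8.3): 0.009998, pass. The 45 are 45/510 = 8.8% of full uses.
- At an assumed 540 full uses, 15 partial uses (2.8%) are enough to change the result.
- At 555 or more full uses, one SADE passes under either reading.

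**Step 7: larger exposure under Rev. 08.** All participants are now offered the long-term phase, which adds 9 rings (S1V2) or 13 rings (V1S2) per woman. Assume everyone counted finishes and the groups split as evenly as possible.
- 60 crossover and 30 long-term completers: 60 × 4 + 15 × 9 + 15 × 13 = 570. One SADE passes (0.0097); two fail (0.0126).
- 60 crossover and 42 long-term completers: 240 + 21 × 9 + 21 × 13 = 702. Two still fail (0.0103).
- All 61 complete both: 61 × 4 + 31 × 9 + 30 × 13 = 913. Up to three pass, since 913 exceeds 874.

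**The case against.** The best defence is that Section 8.3 is a planning illustration. Section 8.5 points to Section 4.2.2, which gives the right answer if the limit is left unrounded, and nothing says the sponsor will round at analysis. The plan expects no SADEs, and zero passes from 368 devices under any reading of the denominator. Exposure may also be well above 510, so the remark that only zero passes is tied to that total. The zero-event limits are true as one-sided statements, and Section 8.3 never calls them two-sided.

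Much of this is fair. The decision rule itself is not wrong, the zero-event point is a labelling matter that changes no result, and at 570 uses one SADE would pass. None of it rescues the 2/510 statement, which is false at the total it names and needs 720 uses to become true. Nor does it settle the denominator. Section 8.3 cannot be read as keeping short uses for event counting only, because it says they push the number of uses evaluated past 553.

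**Conclusion.** The concern holds. At 510 devices the trial's own rule tolerates no SADEs, while Section 8.3 states a tolerance of two. The upper limit for 2/510 is 1.41% and for 1/510 it is 1.09%, against a limit of 1%. The failure of 2/510 does not depend on the choice of exact method, on sidedness, or on pooling with CI01. The failure of 1/510 depends on the two-sided rule that Section 4.2.2 sets.

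Sections 5.3.5 and 8.3 give opposite instructions for the denominator. This can decide the result only when full uses fall short of a threshold in Step 5 and partial uses carry the total across it. The number of partial uses is not given in the documents, so the 45 and 15 above are illustrations. If no SADE occurs, neither problem affects the outcome once 368 uses are reached.

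**What to change.** - **Section 8.3:** give the two-sided Clopper-Pearson upper limits to four decimals: 2/510 0.0141 (fails), 1/510 0.0109 (fails), 0/510 0.0072 and 0/553 0.0066 (both pass). Replace the 2/510 tolerance with the minimum device counts of 368, 555, 720 and 874 for 0, 1, 2 and 3 SADEs, and note that totals under Rev. 08 may exceed 510.
- **Section 4.2.2:** state that the unrounded Clopper-Pearson upper limit is compared with 0.0100.
- **Denominator:** reconcile Sections 5.3.5 and 8.3, and align 4.2.2 and 8.12, to one pre-specified definition. State that counting partial uses makes the criterion easier to meet and excluding them makes it harder.
- **Numerator:** confirm that every SADE counts, in line with Sections 5.3.5 and 5.3.9, and reconcile this with the use-as-instructed restriction in 4.2.2 and 8.12.
- **Timing:** settle this before the blind is broken and before any safety analysis. SADEs reach the sponsor within 24 hours (Section 13), the sponsor holds the randomization schedule (Section 5.4.3), and the long-term phase is open-label (Section 5.3.4). The amendment should therefore also record how many VR101 SADEs were known when the denominator was chosen.

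The cost is wording only, with no extra participants or data. The sponsor gives up the stated tolerance of two SADEs at 510 devices.
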